4.2 Follow up

After the completion of the study analysis at day 28 (+/- 3 days) after radiotherapy, the patients will remain in follow up.

The follow up of will be carried out according to clinical practice, with periodic visits and instrumental assessments, which should performed with the following timepoints:

- Clinical examination every 3 months for the first year, then every 6 months
- Radiological imaging 3 months after RT completion, then every 6 months

Disease free survival of the patients, overall survival, possible side effects and other treatments performed in adjuvant or palliative settings will be collected.

4.3 Duration of study

The duration of the treatment is limited by the completion of adjuvant radiotherapy.

This study will take 24 months to conclude the enrollment of 42 patients.

Follow up of the patients will be carried out according to clinical practice, with periodic visits and

instrumental assessments. Patients' follow-up will continue for 24 months after the end of radiation and patients still alive will be considered as censored.

Therefore, the whole duration of the study (enrollment + follow up) will be 48 months.

First results will be evaluated in an interim-analysis (primary and secondary objectives of before-after RT change in immune populations) at 24 months.

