6. ASSESSMENT OF EFFICACY

Blood samples will be collected at two time point to assess immune-modulating effects of adjuvant radiotherapy.

The following blood cells will be assessed at baseline (day -1) before adjuvant RT and at day 28 (+/- 3) after RT completion:

- circulating T cells CD3+CD8+ and CD3+CD4+
- absolute lymphocyte (ALC) count and neutrophil counts (ANC) and neutrophil/lymphocyte ratio (NLR)
- Treg lymphocytes, defined as CD4+CD25+FOXP3+ or CD4+CD25hi+CD39+ cells.
- Naïve/Memory T lymphocytes CD4+ and CD8+ (defined as CD45RA/CD45RO)
- myeloid-derived suppressor cells, defined as cells expressing Lin-neg (CD3, CD14, CD15, CD19, CD56) /HLA-DR-/CD33+/CD11b+ in either a “lymphocyte” (small FSCxSSC) gate, or in a “monocyte” (larger FSCxSSC) gate, and as HLA-DR+/lo CD14+ cells in a large gate.
- Plasmacytoid Dendritic Cells (CD303+CD123+)
- NK cells dim (CD3-CD16+CD56+) and bright (CD3-CD16-CD56++);
- NKT cells (CD3+CD56+);
- Myeloid Dendritic cells (CD1c+ and CD141+);
- Monocyte subsets (classical CD14+CD16-, intermediate CD14+CD16+, non classical CD14+/-CD16+);
- B lymphocytes (CD19+);
- Analysis of plasma cytokines (TNFalpha, TGFbeta, IL-6, IL-10) by ELISA;
- IFN signature: real-time PCR on mRNA from PBMCs

A centralized evaluation of all blood and tissue samples collected will be performed at the Department of Molecular and Translational Medicine, Oncological-Immunological Experimental Section, University of Brescia.

Follow up of all subjects enrolled will be conducted according to clinical practice, with periodic visits and instrumental assessments. Survival status of the patients and possible other treatments performed will be collected for at least 24 months.

Plasma and mRNAs will be stored at the Department of Molecular and Translational Medicine, Oncological-Immunological Experimental Section, University of Brescia. All samples will be identified by a specific numerical code.

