10.1 Sample size calculations

To test the Hazard Ratio between Group0 (patients with ALC less than 500 cells/mL) and Group1 (patients with ALC greater than 500 cells/mL) of 0.3 with type I error rate of 5% and power of 80%, we need a minimum of 23 total events which in our hypothesis of median survival time in Group 0 equal to 18 months, 5% censoring rate and whole duration of the study of 4 years correspond to 42 patients, 17 in the Group0 and 25 in the Group1..

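### Section 4.3 and the schedule end each patient's DFS follow-up 24 months after radiotherapy although the study runs to month 48; this gives up about a fifth of the expected events, and other sections disagree on the length.

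*Combined protocol and SAP*

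**What the plan says.** Section 4.3 states that "follow-up will continue for 24 months after the end of radiation"; patients who are alive at that point count as censored. Enrolment takes 24 months ("This study will take 24 months to conclude the enrollment of 42 patients"), and the section concludes that "the whole duration of the study (enrollment + follow up) will be 48 months". The schedule of evaluation has one follow-up column, at 24 months, and DFS and OS are recorded only there.

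Three other places do not match this:

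- Section 6: "Survival status of the patients and possible other treatments performed will be collected for at least 24 months". This is a floor, and it does not name DFS.
- Section 4.2: clinical examinations and imaging settle to every six months, with no end date, and DFS and OS are to be collected.
- Section 10.1: "we need a minimum of 23 total events", obtained from 42 patients (17 and 25) on the assumptions of "median survival time in Group 0 equal to 18 months, 5% censoring rate and whole duration of the study of 4 years".

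**The concern.** The primary test is a Cox comparison of DFS by lymphocyte count after radiotherapy, and its power depends on the number of events. Under Section 4.3 a patient enrolled in the first month is closed at about month 26, while the study continues for nearly two more years for the last patients. Any recurrence in that interval is not counted, although the patient is still attending the routine visits of Section 4.2. A site reading Sections 4.2, 4.3 and 6 together cannot tell whether a recurrence at month 30 belongs in the primary analysis.

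The rule also fits poorly with the plan's own reasoning. Section 10 draws its effect from 3-year recurrence-free survival, yet under the cap no patient is observed to three years after radiotherapy. Finally, the only censoring rule given refers to patients still alive. That is a rule for OS and does not say when a patient without recurrence is censored for DFS.

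**Working it through.** **Inputs from the documents.** Hazard ratio 0.3, 5% type I error, 80% power, 17 + 25 patients, Group 0 median 18 months, 5% censoring, 4 years (Section 10.1); hazard ratio 0.45 (Section 10); 24 months' enrolment, 24 months' follow-up after radiotherapy, 48 months in all (Section 4.3).

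**Assumptions.** Uniform accrual; exponential DFS counted from the end of radiotherapy; radiotherapy lasting 1.5 months (30 fractions, Section 1.2, at five per week); two-sided test; no dropout unless stated.

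**Step 1: the plan's own figures.** With p = 17/42, p(1−p) = 0.2409. Schoenfeld events = (1.96 + 0.842)² / [0.2409 × (ln 0.3)²] = 7.849 / (0.2409 × 1.4496) = 22.5, rounded up to 23. This agrees with Section 10.1.

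The hazards are λ₀ = ln 2 / 18 = 0.0385 and λ₁ = 0.3 × λ₀ = 0.01155 per month. If every patient is followed for 48 months with 5% censoring per year, 23 events need 41.9 patients, which matches 42. A 24-month cap needs 59 to 65 patients, depending on how the 5% is applied. Accrual over 24 months with everyone followed to month 48 needs 46 to 52. So 42 is reproduced with about 48 months of follow-up per patient, not by the rule in Section 4.3.

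**Step 2: follow-up given up.** For a patient enrolled at month u, the extra time to month 48 is max(0, 48 − 1.5 − 24 − u) = max(0, 22.5 − u). It is about 22 months for the first patient and nil for the last. The mean is (22.5²/2)/24 = 10.5 months.

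**Step 3: events under the cap (hazard ratio 0.3).**

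- Group 0: 17 × (1 − e^(−0.0385×24)) = 10.25
- Group 1: 25 × (1 − e^(−0.01155×24)) = 6.05
- Total 16.3 (16.28 after allowing for the last enrollees, who reach month 48 just short of 24 months)

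**Step 4: events with close-out at month 48.** Averaged over accrual, the event probability is 1 − [e^(−22.5λ) − e^(−46.5λ)] / (24λ).

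- Group 0: 17 × 0.7256 = 12.34
- Group 1: 25 × 0.3265 = 8.16
- Total 20.5

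The loss is 4.2 events, and 4.21/20.50 = 20.6%.

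**Step 5: power.** Power = Φ(√(d × 0.2409) × |ln HR| − 1.96).

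- Cap: √(16.28 × 0.2409) × 1.204 − 1.96 = 0.42, giving 66%
- Month 48: √(20.50 × 0.2409) × 1.204 − 1.96 = 0.72, giving 76%

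A log-rank simulation of 20,000 trials gave 69% and 79%.

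**Step 6: sensitivity.**

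| Case | Events, cap | Events, month 48 | Share lost | Schoenfeld power |
|---|---|---|---|---|
| HR 0.3 | 16.3 | 20.5 | 20.6% | 66% v 76% |
| HR 0.3, RT 2 months | 16.3 | 20.3 | 19.9% | 66% v 76% |
| HR 0.3, 5% per year censoring | 15.6 | 19.3 | 19% | 64% v 74% |
| HR 0.45 | 18.7 | 23.5 | 20% | 40% v 48% |

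The 23.5 events in the last row do not meet the requirement: at a hazard ratio of 0.45 the formula of Step 1 asks for 52.

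If the hazard after month 24 were half the earlier value (replace λT by 24λ + 0.5λ(T − 24) beyond month 24), the month-48 total at hazard ratio 0.3 would be 18.6 rather than 20.5.

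**The case against.** The strongest reply is that the cap is only one reading. Section 6 gives a minimum, Section 4.2 has no end date, Section 10.1 assumes four years, and the censoring clause in Section 4.3 is OS wording. This stands in part: a reader might infer that the documents settle on a cap, and they do not. But Section 6 leaves DFS out, and the two places that fix when follow-up ends or DFS is recorded (Section 4.3 and the schedule) both say 24 months. The cap is therefore the better reading for the primary outcome. If longer follow-up was meant, the text still has to be corrected.

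Second, a fixed horizon is legitimate. It suits the 2-year OS outcome and gives every patient the same window. That is true, and a 24-month rule is not an error in itself. The difficulty is that it does not supply the events on which 42 patients were justified.

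Third, the gain depends on a constant hazard after month 24. Section 1.2 quotes loco-regional control of 88% at 2 years and 82% at 5 years, a pattern with fewer late events. Applied to 42 patients, those rates give 5.0 events under the cap and 5.8 with a month-48 close-out, a loss of 13%. Loco-regional control is not DFS, so this shows the sensitivity without replacing the estimate.

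A reader might also infer that a common close-out restores most of the missing power. The figures do not support that: at a hazard ratio of 0.3 the events still fall short of 23, and at 0.45 power stays below 50% by the formula and reaches only about 50% by simulation.

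**Conclusion.** The point holds as an inconsistency in the length of follow-up with a real, moderate cost. Read as written for DFS, Section 4.3 and the schedule give up 10.5 months of follow-up per patient on average. That is about 4 of 20.5 expected events, and about 10 points of power at a hazard ratio of 0.3 or 8 points at 0.45. The share lost is 18% to 21% across hazard ratios of 0.3 or 0.45, radiotherapy of 1.5 or 2 months, and no censoring or 5% per year. It rests on uniform accrual and a constant hazard, and would be smaller if recurrences concentrate in the first two years. Following everyone to a common date is worth doing but is a partial remedy: it does not deliver the 23 events of Section 10.1, and it does not make the study adequately powered at a hazard ratio of 0.45.

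**What to change.** Replace the follow-up and censoring sentence in Section 4.3 with:

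> All patients are followed for DFS and OS to one common cut-off date, 48 months after the first enrolment. Patients without a DFS event are censored for DFS at their last disease assessment on or before the cut-off. Patients alive are censored for OS at the date last known alive.

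An alternative cut-off is the date on which the last enrolled patient reaches 24 months after the end of radiotherapy. That is about month 24 + 1.5 + 24 = 49.5, with about 21 expected events and 77% Schoenfeld power at a hazard ratio of 0.3. Either way the date must be defined explicitly.

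Then:

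- align Section 6 and the schedule with this rule, naming DFS in both;
- report 24-month DFS and 2-year OS as Kaplan-Meier estimates;
- restate in Section 10.1 the expected events and power under the chosen rule, including the shortfall against 23.

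The cost is protocol wording and extra data entry from the six-monthly visits already in Section 4.2. Follow-up will differ in length between patients, which Cox regression accommodates. The alternative cut-off extends the study about 1.5 months past month 48. No additional patients or new type of visit are needed.

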4.4 Numbers of subjects

Patients with high risk cSCC will be included. The study is a multicentric study and will enroll 42 subjects in Italy.

5. STUDY TREATMENT

5.1. RT technique

Radiotherapy adjuvant treatment will be established during multidisciplinary team discussion taking into account patients and disease characteristics and conducted as per clinical practice. A preliminary visit and a treatment planning will be performed. Multiple RT modalities are allowed in relation to site, dimension and shape of RT field: eg MV (megavoltage) electrons or different techniques using photons (eg Helical or volumetric IMRT; with/without Image guided treatment).

The objective of the RT planning will be obtaining a uniform dose distribution to the target, minimizing the dose to surrounding healthy tissues. Simulation, treatment planning, treatment delivery and verification should be performed according to standard practice.

A high-risk tumor volume for the primary tumor (CTVp_{HR}) and nodal disease (CTVn_{HR}) should be recognized in the delineation phase based on all clinical, radiological and pathological findings, enlarged of a 5-mm margin (edited for anatomical barriers) and be targeted to a total dose of 60 Gy at conventional fractionation, whereas those areas deemed at substantial risk of microscopic disease such as positive surgical margin or pathologic lymphnodes with extranodal extension may warrant a boost dose up to 66 Gy (CTVp_{HR_Boost} or CTVn_{HR_Boost}).

Adequate information and medication to prevent and managed side effects will be provided during visits and treatment.

The Head and Neck Cancer International Group (HNCIG) Consensus Guidelines (8) should be regarded as the reference paper for the delivery of postoperative RT in high-risk cutaneous squamous cell carcinoma of the head and neck.

5.2. Concomitant medications

With the exception of the prohibited drugs listed in the section 5.3, concomitant drugs are permitted.

5.3. Prohibited Medications

The following medications are prohibited while the subject is in this study:

- Other anti-cancer therapies, except for chronic hematological malignancies
- Investigational/experimental medicines or vaccines
- Other radiotherapeutic treatment in the 28 days before study enrollment

6. ASSESSMENT OF EFFICACY

Blood samples will be collected at two time point to assess immune-modulating effects of adjuvant radiotherapy.

The following blood cells will be assessed at baseline (day -1) before adjuvant RT and at day 28 (+/- 3) after RT completion:

- circulating T cells CD3+CD8+ and CD3+CD4+
- absolute lymphocyte (ALC) count and neutrophil counts (ANC) and neutrophil/lymphocyte ratio (NLR)
- Treg lymphocytes, defined as CD4+CD25+FOXP3+ or CD4+CD25hi+CD39+ cells.
- Naïve/Memory T lymphocytes CD4+ and CD8+ (defined as CD45RA/CD45RO)
- myeloid-derived suppressor cells, defined as cells expressing Lin-neg (CD3, CD14, CD15, CD19, CD56) /HLA-DR-/CD33+/CD11b+ in either a “lymphocyte” (small FSCxSSC) gate, or in a “monocyte” (larger FSCxSSC) gate, and as HLA-DR+/lo CD14+ cells in a large gate.
- Plasmacytoid Dendritic Cells (CD303+CD123+)
- NK cells dim (CD3-CD16+CD56+) and bright (CD3-CD16-CD56++);
- NKT cells (CD3+CD56+);
- Myeloid Dendritic cells (CD1c+ and CD141+);
- Monocyte subsets (classical CD14+CD16-, intermediate CD14+CD16+, non classical CD14+/-CD16+);
- B lymphocytes (CD19+);
- Analysis of plasma cytokines (TNFalpha, TGFbeta, IL-6, IL-10) by ELISA;
- IFN signature: real-time PCR on mRNA from PBMCs

A centralized evaluation of all blood and tissue samples collected will be performed at the Department of Molecular and Translational Medicine, Oncological-Immunological Experimental Section, University of Brescia.

Follow up of all subjects enrolled will be conducted according to clinical practice, with periodic visits and instrumental assessments. Survival status of the patients and possible other treatments performed will be collected for at least 24 months.

Plasma and mRNAs will be stored at the Department of Molecular and Translational Medicine, Oncological-Immunological Experimental Section, University of Brescia. All samples will be identified by a specific numerical code.

7. ASSESSMENT OF ADVERSE EVENTS

Per regulatory requirements, if an event is assessed by the Sponsor Institution as a Serious Unexpected Adverse Reaction (SUSAR), even there is no experimental drug tested in the protocol, it is the responsibility of the Sponsor Institution to submit the SUSAR to Regulatory Authorities according to applicable regulations.

In addition, the SUSAR will be distributed to the Investigators/sites utilizing a Council for International Organizations of Medical Sciences (CIOMS) report form, or the MedWatch 3500A form). The Investigator/site will submit a copy of the report to their respective Institutional Review Board (IRB) or Independent Ethics Committee (IEC) per the governing institutional requirements and in compliance with local laws and guidelines.

8. DATA MANAGEMENT

A full dataset will be collected for all patients enrolled. Qualified study staff will perform collection of the findings derived from the centralized blood samples examination.

8.1 Data confidentiality

Information about study subjects will be kept confidential and managed under the applicable laws and regulations. Those regulations require a signed subject authorization informing the subject of the following:

- What protected health information (PHI) will be collected from subjects in this study
- Who will have access to that information and why
- Who will use or disclose that information
- The rights of a research subject to revoke their authorization for use of their PHI.

In the event that a subject revokes authorization, the Investigator, by regulation, retains the ability to use all information collected prior to the revocation of subject authorization. For subjects that have revoked authorization, attempts should be made to obtain permission to collect follow-up safety information (e.g. has the subject experienced any new or worsened AEs) at the end of their scheduled study period.

8.2 Source Documentation

The Investigator is responsible for ensuring that the source data are accurate, legible, contemporaneous, original and attributable, whether the data are hand-written on paper or entered electronically. If source data are created (first entered), modified, maintained, archived, retrieved, or transmitted electronically via computerized systems (and/or any other kind of electronic devices) as part of regulated clinical trial activities, such systems must be compliant with all applicable laws and regulations governing use of electronic records and/or electronic signatures. Such systems may include, but are not limited to, electronic medical/health records (EMRs/EHRs), adverse event tracking/reporting, protocol required assessments, and/or drug accountability records).

When paper records from such systems are used in place of electronic format to perform regulated activities, such paper records should be certified copies. A certified copy consists of a copy of original information that has been verified, as indicated by a dated signature, as an exact copy having all of the same attributes and information as the original.

8.3 Investigational Site Training

The Sponsor will provide quality investigational staff training prior to study initiation. Training topics will include but are not limited to: GCP, AE reporting, study details and procedure, electronic CRFs, study documentation, informed consent, and enrollment of WOCBP.

Access to the system will be controlled by a sequence of individually assigned user identification codes and passwords, made available only to authorized personnel who have completed prerequisite training.

8.4 Site monitoring

Before study initiation, at a site initiation visit or at an investigator's meeting, Sponsor personnel (or designated CRO) will review the protocol and CRFs with the investigators and their staff. During the study, the field monitor will visit the site regularly to check the completeness of patient records, the accuracy of entries on the CRFs, the adherence to the protocol to Good Clinical Practice, the progress of enrollment, and to ensure that study treatment is being stored, dispensed, and accounted according to specifications. Key study personnel must be available to assist the field monitor during these visits.

The investigator must maintain source documents for each patient in the study, consisting of case and visit notes (hospital or clinic medical records) containing demographic and medical information, laboratory data, electrocardiograms and the results of any other tests or assessments. All information recorded on CRFs must be traceable to source documents in the patient's file.

The investigator must also keep the original signed informed consent form (a signed copy is given to the patient). The investigator must give the monitor access to all relevant source documents to confirm their consistency with the CRF entries. The Sponsor monitoring standards require full verification for the presence of informed consent, adherence to the inclusion/exclusion criteria and documentation of SAEs.

In addition, the study may be evaluated by the Sponsor internal auditors and inspectors from Competent authority who must be allowed access to CRFs, source documents, other study files, and study facilities. the Sponsor audit reports will be kept confidential.

The investigator must notify the Sponsor promptly of any inspections scheduled by regulatory authorities, and promptly forward copies of inspection reports to the Sponsor.

8.5 Data collection

This study will use an Electronic Data Capture (EDC) system. The designated investigator staff will enter the data required by the protocol into the Electronic Case Report Forms (eCRF). The eCRFs have been built using a fully validated secure web-enabled software that conforms to FDA requirements. Investigator site staff will not be given access to the EDC system until they have been trained. Automatic validation programs check for data discrepancies in the eCRFs allow modification or verification of the entered data by the investigator staff.

The Principal Investigator is responsible for assuring that the data entered into eCRF is complete, accurate, and that entry and updates are performed in a timely manner.

8.6 Database management and quality control

The Sponsor personnel (or designated CRO) will review the data entered by investigational staff for completeness and accuracy. Electronic data queries stating the nature of the problem and requesting clarification will be created for discrepancies and missing values and sent to the investigational site via the EDC system. Designated investigator site staff are required to respond promptly to queries and to make any necessary changes to the data. Medical history/current medical conditions and adverse events will be coded using the Medical dictionary for regulatory activities (MedDRA) terminology. The occurrence of any protocol violations will be determined. After the data has been verified to be complete and accurate, the database will be declared locked. Authorization is required prior to making any database changes to locked data, by joint written agreement between the Biostatistics and Data Management and the Sponsor.

8.7 Study governance and oversight

The safety of the study is closely monitored on an ongoing basis by the Sponsor representative and the coordinating investigator in consultation with Sponsor's representatives. Issues identified will be addressed; for instance, this could involve amendments to the study protocol and letters to Investigators.

